3.2 Analysis Populations

3.2.1 *Intent-to-Treat (ITT) Population*

The ITT Population is defined as all participants randomized into the study. Treatment classification will be based on the randomized treatment.

3.2.2 *Modified Intent-to-Treat (mITT) Population*

The mITT Population is defined as all participants in the ITT Population who receive at least 1 dose of any study drug and have a baseline value for the LDL-C assessment. Any efficacy measurement obtained during the Safety Follow-up Visit (Visit 5; Day 112) after a participant permanently discontinues the study drug or after a participant receives an excluded medication and/or procedure will be removed from the mITT analysis. Treatment classification will be based on the randomized treatment. The mITT Population will be used for the primary analysis of all efficacy endpoints.

3.2.3 *Per-Protocol (PP) Population*

The PP Population is defined as all participants in the mITT Population who have a Day 84 value for the LDL-C assessment, and who did not experience a major protocol deviation that could potentially impact the primary efficacy endpoint. The PP Population, along with the reason for exclusion, will be finalized prior to study unblinding.

3.2.4 *Pharmacokinetic (PK) Population*

The PK Population is defined as all participants in the mITT Population who have sufficient blood samples collected for valid estimation of PK parameters.

3.2.5 *Safety Population*

The Safety Population is defined as all participants who receive at least 1 dose of any study drug. Treatment classification will be based on the actual treatment received. The Safety Population will be the primary population used for the safety analysis.

3.3 Subject Data and Study Conduct

3.3.1 *Subject Disposition*

Subject disposition will be presented for all randomized participants. Counts and percentages of participants who are randomized, complete the treatment, discontinue treatment (including primary reason for discontinuation), complete the study, prematurely discontinue from the study (including primary reason for discontinuation) will be summarized by treatment group and overall. For each scheduled visit, counts and percentages of participants who do not complete the visit, partially complete the visit in-person, or complete the visit virtually will be summarized by treatment group and overall. The denominator for calculating percentages will be based on the number of randomized participants.

Data listings for subject disposition and exclusion and inclusion criteria violations will be provided.

3.3.2 *Protocol Deviations*

Protocol deviations will be identified based on the clinical data as defined in the Protocol Deviation Plan. The Protocol Deviation Plan will define all protocol deviations as either CSR reportable or non-CSR reportable deviations. Counts and percentages of participants with CSR reportable protocol deviations by deviation category will be summarized by treatment group and in total based on all randomized participants. A listing of CSR-reportable protocol deviations will be generated.

3.3.3 *Analysis Populations*

Counts and percentages of participants in each analysis population will be summarized by treatment group and overall based on all randomized participants. Reasons for exclusion from the PP Population will also be summarized.

A listing detail participants inclusion in each of the study populations will be provided.

3.3.4 *Demographic and Baseline Characteristics*

Demographic and baseline characteristics including age, race, ethnicity, sex, height, weight, body mass index (BMI), and stratification group (LDL-C value ≥ 100 or < 100 mg/dL) will be summarized with descriptive statistics or counts and percentages of participants as appropriate by treatment group and overall, for the mITT Population. If they differ from the mITT Population, summaries will also be provided for the ITT Population, the PP Population, and the Safety Population.

All demographic and baseline characteristic data will be provided in participant listings.

3.3.5 *Medical History*

Medical history will be coded to system organ class and preferred term using the Medical Dictionary for Regulatory Activities (MedDRA) version 24.1. Counts and percentages of participants with medical history by system organ class (SOC) and preferred term (PT) will be summarized by treatment and overall based on all randomized participants.

A listing of all medical history data will be provided.

3.3.6 Concomitant Medications

Medication start and stop dates that are recorded on the Prior & Concomitant Medications case report form will be used to determine whether the medications are prior or concomitant to the study treatment. Concomitant medications are defined as those used on or after the first dose of study drug. Prior medications are defined as those used prior to and stopped before the first dose of study drug. All prior and concomitant medication verbatim terms will be coded using the World Health Organization (WHO) Drug Dictionary (WHO Drug B3 Global, September 2021). The numbers and percentages of participants taking prior and concomitant medications in each treatment group and overall will be summarized by anatomical therapeutic chemical (ATC) class and preferred term for the Safety Population.

All medications will be listed and flagged as either prior or concomitant.

3.3.7 Study Drug Exposure and Compliance

Participants' exposure to randomized study drug will be summarized with descriptive statistics for the Safety Population. Days of exposure is defined as:

$$\text{date of last dose of study drug} - \text{date of first dose} + 1$$

For those whose date of first dose from the initial blister card dispensed was not available, the date of randomization will be used to assign the date of first dose. For those who failed to provide the date of last dose of study drug, the earliest date between the end of treatment date and the date of end of study/early termination will be used.

A summary will be provided to display counts and percentages of participants in each treatment with exposure in the following categories: <4 weeks, 4 – <8 weeks, 8 - <12 weeks and 12+ weeks.

Summary statistics will be presented for overall compliance to study drug by treatment group and in total. Counts and percentages of participants will also be tabulated by groups with overall compliance < 80%, 80% to 120%, and > 120%.

The percent overall compliance to obicetrapib tablets will be calculated as:

$$100 \times \frac{\text{actual tablets taken}}{\text{expected study drug taken}},$$

The percent overall compliance to ezetimibe capsules will be calculated as:

$$100 \times \frac{\text{actual capsules taken}}{\text{expected study drug taken}},$$

The percent overall compliance to study drug will be calculated as:

$$100 \times \frac{\text{actual study drug taken}}{\text{expected study drug taken} \times 2},$$

Expected study drug taken = (the earliest date between the end of treatment date and the date of early termination) – the date of randomization +1.

The actual study drug taken is reported on the electronic case report form (eCRF). If no kits are returned, it will be assumed that all study drug from that kit were used.

Listings of drug accountability and derived exposure and compliance will be provided for all randomized participants.

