# 5.5.2 Study Drug Preparation and Dispensing

The study drugs include obicetrapib 10 mg, ezetimibe 10 mg, and matching placebo for each. Participants will be randomized to receive combination therapy (obicetrapib 10 mg + ezetimibe 10 mg [administered as one 10 mg obicetrapib tablet and one 10 mg ezetimibe capsule]); obicetrapib monotherapy (obicetrapib 10 mg [administered as one 10 mg obicetrapib tablet and 1 placebo capsule]), or placebo (administered as 1 placebo tablet and 1 placebo capsule) on Day 1 to Day 84. Study drugs (1 tablet and 1 capsule) will be administered by the participant orally with water, once daily on Day 1 to Day 84 at approximately the same time each morning.

At Visit 2 (Day 1), participants will receive 1 kit (containing 32 obicetrapib tablets or matching placebo tablets and 32 ezetimibe capsules or matching placebo capsules totaling 64 tablets/capsules per kit) with the study drugs appropriate for the participant's treatment group. At Visit 3 (Day 28), participants will receive 2 kits as described above. Each kit will provide a sufficient supply for 28 days of dosing, with enough for an extra 4 days of dosing in case the participant needs to postpone the next visit. Participants will be instructed to take 2 units from the kit each day. The kit will be clearly labelled to indicate which tablets/capsules to use on each day. Participants will be instructed to bring all unused study drugs to the site at the next visit.

This study protocol includes contingency measures to manage disruptions due to COVID-19 control measures, including modifications to study drug dispensation specific to situations where COVID-19 is impacting study conduct. See Section 3.1.4 for details of COVID-19 contingency measures. In the absence of a COVID-19 impact, it is expected that Investigators and participants follow the protocol requirements as set forth.

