## 5.5.3 Study Drug Administration

Study drugs (1 tablet and 1 capsule) will be administered by the participant orally with water, once daily on Day 1 to Day 84 at approximately the same time each morning. On days with visits scheduled, study drugs should be administered with water following all fasted blood samples. At Visits 3 and 4, participants will dose from the kit received at the previous visit (Visits 2 and 3, respectively).

If a participant forgets to take study drug on a given day, they should take the next dose as normal and should not take a double dose to make up for the forgotten dose.

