## 5.5.4 Treatment Compliance

Compliance to the study drug regimen will be evaluated by counting unused tablets and capsules. Participants will be instructed to bring all unused study drugs to the site at Visits 3 and 4. During the Treatment Period, if compliance is not between 80% and 120%, inclusive, the participant will be counselled about the importance of compliance to the regimen. If the limits are exceeded at 2 consecutive visits, a decision will be made by the Investigator and Sponsor as to whether the participant should be withdrawn from the study.

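### SAP 3.3.7 scores unreturned kits as fully taken, so a completer who returns nothing is tabulated at about 114% compliance, inside the 80–120% band, whatever was actually taken

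*SAP*

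**What the plan says.** Protocol 5.5.4 sets the method: "Compliance to the study drug regimen will be evaluated by counting unused tablets and capsules". It uses 80% to 120%, inclusive, as the range outside which sites counsel the participant.

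SAP 3.3.7 divides units taken by units expected, with one formula each for tablets, capsules and study drug in total. Units taken come from the eCRF, with the fallback "If no kits are returned, it will be assumed that all study drug from that kit were used". Expected days run from randomization to the earlier of the end-of-treatment date and the early-termination date, counting both ends. Participants are then tabulated by "overall compliance < 80%, 80% to 120%, and > 120" percent. Drug accountability and derived compliance are also listed for everyone randomized.

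Protocol 5.5.2 gives the supply. A kit is described as "containing 32 obicetrapib tablets or matching placebo tablets and 32 ezetimibe capsules or matching placebo capsules totaling 64 tablets/capsules per kit". On timing, "At Visit 2 (Day 1), participants will receive 1 kit" and "At Visit 3 (Day 28), participants will receive 2 kits as described above". On overage, "Each kit will provide a sufficient supply for 28 days of dosing, with enough for an extra 4 days of dosing". Protocol 5.5.3 has dosing "once daily on Day 1 to Day 84 at approximately the same time each morning".

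Neither document provides a category for unknown compliance, a flag for values filled in under the fallback, or a summary that leaves those values out.

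**The concern.** Compliance here is a returned-unit count. When a kit does not come back there is no count, and the SAP fills the gap with the largest value possible, including the 4 spare days that the participant was never expected to take. The score then depends on how many kits were dispensed and how long the participant stayed, not on what was swallowed.

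At stake is the table that tells a reader whether each arm took its assigned drug. A completer with unknown intake is shown as acceptably compliant, and one who took every dose but returned nothing is shown as over-using. Someone who leaves early with kits in hand can be shown as a gross over-user. None of these entries can be told apart from a counted value in the summary.

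**Working it through.** **Inputs.** Kit contents, dispensing schedule and overage: Protocol 5.5.2. Dosing period: Protocol 5.5.3. Day 84 window of ±2 days: Protocol 3.1.2. Formulas, denominator, fallback and bands: SAP 3.3.7.

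**Step 1, the plan's own figure.** (28 + 4) days × 2 units per day = 64 units per kit. This matches Protocol 5.5.2.

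**Step 2, supply to a completer.** 1 kit on Day 1 plus 2 on Day 28 = 3 kits; 3 × 32 = 96 tablets and 96 capsules; 3 × 64 = 192 units.

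**Step 3, completer who returns nothing.** Total compliance = 100 × units taken / (2 × expected days). With the end-of-treatment date at Day 84, expected days = 84 − 1 + 1 = 84, so 100 × 192 / 168 = 114.3%. Tablets and capsules separately give 96 / 84 = 114.3%.

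| Day of end of treatment | Tabulated compliance |
|---|---|
| 82 | 96 / 82 = 117.1% |
| 83 | 96 / 83 = 115.7% |
| 84 | 96 / 84 = 114.3% |
| 85 | 96 / 85 = 112.9% |
| 86 | 96 / 86 = 111.6% |

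Every value is inside 80–120%. True intake does not appear in the calculation, so 0% and 100% give the same entry.

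**Step 4, partial non-return with otherwise perfect dosing at Day 84.** First kit missing: (32 + 56) / 84 = 104.8%. Both Day 28 kits missing: (28 + 64) / 84 = 109.5%. The true value in each case is 100%.

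**Step 5, early termination with nothing returned, denominator ending at the termination visit.** With three kits the score exceeds 120% when expected days are below 96 / 1.2 = 80; examples are Day 40, 96 / 40 = 240%, and Day 56, 96 / 56 = 171.4%. With only the first kit dispensed, the threshold is 32 / 1.2 = 26.7 days; at Day 14 the score is 32 / 14 = 228.6%.

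**Two points of reading.** The fallback moves from no kits to a single kit within one sentence; I read it per kit. For someone who returns nothing, either reading gives 192 units. The SAP does not define the end-of-treatment date; I took it as the Day 84 visit or last scheduled dose. SAP 3.3.7 uses that date as a substitute when the last-dose date is missing, which suggests that it is a separate item but does not settle the matter.

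**The case against.** The strongest reply is that little depends on this number. No efficacy model in SAP 3.4 uses compliance. The fallback changes a derived percentage, not the record: SAP 3.3.7 lists accountability for everyone randomized, Protocol 5.5.5 requires returns to be documented and discrepancies reconciled, exposure is summarized separately from dose dates, and obicetrapib concentrations on Days 28 and 84 give a partial check in the two obicetrapib arms. Participants are told to bring unused drug back, and the documents give no expected rate of non-return. All of this stands. It limits the consequence but does not make the tabulated value right, because the listings do not correct the summary.

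Several stronger readings are tempting, and the documents do not support them.

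- **That the Per-Protocol set is contaminated.** SAP 3.2.3 excludes participants with major deviations that could affect the primary endpoint, but SAP 3.3.2 leaves the definition of deviations to a Protocol Deviation Plan that is not available. Whether compliance enters it cannot be seen.
- **That non-returners are the least adherent.** Nothing in the documents says so. Their intake is unknown, and no more can be claimed.
- **That someone who took 10 doses and kept the two Day 28 kits is scored as compliant.** (10 + 64) / 84 = 88.1%, against a true 10 / 84 = 11.9%, holds only with an 84-day denominator. If the end-of-treatment date were the last dose, the score would be 74 / 10 = 740%, outside the band. In either case the returned first kit would show about 10 / 28 = 36% at Visit 3.
- **That the first interval alone scores 32 / 28 = 114.3%.** The SAP defines no per-interval compliance.
- **That good tablet use can mask poor capsule use.** Under a pooled figure, (100 + 60) / 2 = 80% would be in band. But SAP 3.3.7 calls all three percentages overall compliance, so which of them the bands apply to is ambiguous.

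**Conclusion.** The point holds as a defect in a descriptive summary. An explicit rule gives a completer who returns none of three kits a score of 114.3% (111.6% to 117.1% across the visit window), in band whatever the true intake. This assumes an end-of-treatment date at about Day 84.

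Because the rule credits the maximum possible intake, an affected participant's percentage cannot fall below the true value on the same denominator. The effect on the in-band proportion is not one-directional: completers are held inside the band, while early terminators with three kits and fewer than 80 expected days go above it, if the denominator ends at the termination visit.

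The number of participants affected cannot be estimated from the documents. The primary mITT result is untouched, and an effect on the Per-Protocol analysis is neither shown nor excluded. The correction is worth making because it is cheap and the current sentence needs rewording in any case.

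**What to change.** Replace the fallback sentence in SAP 3.3.7 with:

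> If any dispensed kit is not returned and the eCRF has no count of units taken, overall compliance is not evaluable and the participant is counted in a separate row, not evaluable (kit not returned), by treatment group.

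This works at participant level, as it must: the SAP has no interval compliance, and the second and third kits are dispensed together.

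As a supporting summary, repeat the band counts with unreturned units taken as 0% and then as 100% of the doses expected from those kits, leaving out spare units. For a Day 84 completer who returns nothing, the bounds are 0 / 84 = 0% and 84 / 84 = 100%. If only the two Day 28 kits are missing and the first shows 28 doses taken, they are 28 / 84 = 33.3% and (28 + 56) / 84 = 100%.

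Define the end-of-treatment date in the denominator once, for all participants. State that the three bands are shown for tablets, capsules and the total.

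The cost is SAP wording, a few extra table rows and a possibly lower reported compliance rate. No new data are needed and study conduct does not change.

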3.4 Efficacy Assessment

The mITT Population will be the primary population for the efficacy analyses. Efficacy will also be analyzed using the ITT Population and the PP Population as supportive analyses for selected endpoints.

LDL-C will be collected using the following approaches:

1. At each scheduled visit, LDL-C will be calculated using the Friedewald equation unless triglycerides ≥ 400 mg/dL or LDL-C ≤ 50 mg/dL; in both cases, LDL-C level will be measured directly by preparative ultracentrifugation (PUC), also referred to as beta quantification.
2. In addition, for all participants, LDL-C will be measured by PUC, at baseline (Visit 2, Day 1) and at the end of the 12-week Treatment Period (Visit 4, Day 84).

3.4.1 Primary Efficacy Endpoints

Primary Analysis

The primary efficacy endpoint is the percent change from Day 1 to Day 84 in LDL-C (as determined by approach 1 above) for the combination treatment group compared to the placebo group. The percent change will be calculated from Day 1 (Baseline) to each measurement taken at Day 28 and Day 84.

The percent change in LDL-C from Day 1 to Day 84 for each treatment group is defined mathematically as μ_j , where j stands for the j^{th} treatment ($j=0,1,2$) and the subscript 0 refers to the placebo group. The hypotheses testing to the percent change in LDL-C from Day 1 to Day 84 is then defined statistically as following:

$$H_0: \mu_j - \mu_0 = 0, H_1: \mu_j - \mu_0 \neq 0, \text{ where } j=1,2$$

LDL-C values will be summarized by visit and treatment group; visit values, change from baseline and percent change from baseline will be summarized. Missing data patterns in the LDL-C values will also be summarized by treatment group.

The analysis of the percent change from Day 1 to Day 84 in LDL-C will be performed using a mixed model for repeated measures (MMRM) approach. The analysis will include fixed effects for treatment, visit, and treatment-by-visit interaction, along with a covariate of the baseline value as a continuous covariate. Randomization was stratified according to Screening Visit LDL-C value (≥ 100 or < 100 mg/dL) to ensure a similar distribution of LDL-C values across all treatment groups. However, the MMRM model will include the original scale of the baseline LDL-C values as continuous covariate.

The Restricted Maximum Likelihood estimation approach (REML) will be used with an unstructured covariance matrix. The least-squares means (LSMean), standard errors, and 2-sided 95% confidence intervals for the combination treatment group and for the comparison of the combination treatment group to the placebo group will be provided.

The MMRM approach will include all available assessments of percent change in LDL-C from Day 1 to Day 28 and Day 84. The model assumes that the data are missing at random (MAR). If any data are missing, the model will use all information from the other time points to estimate the mean treatment difference at the given time point. No imputation of missing data will be performed for the primary analysis.

The primary analysis will be conducted for the mITT, ITT, and PP Populations.

The analysis will be implemented using SAS® Proc Mixed. The sample SAS code can be found below:

```
*****
```

Note:

USUBJID = unique subject identifier

TREATMENT = 0 (Placebo), 1 (Obicetrapib monotherapy), 2 (Combination therapy)

VISIT = visit

BASE = Baseline value

PCHG = Percent change from Baseline

```
*****
```

proc mixed;

class USUBJID TREATMENT VISIT;

model PCHG = TREATMENT BASE VISIT TREATMENT*VISIT / solution cl;

Repeated VISIT / TYPE=UN sub=USUBJID;

lsmeans VISIT*TREATMENT / cl diff;

run;

```
*****
```

Sensitivity Analyses

Four sensitivity analyses will be performed for the primary efficacy endpoint:

1. MMRM with imputation
2. Analysis of Covariance (ANCOVA)
3. ANCOVA using LDL-C by PUC only
4. MMRM (no imputation) using LDL-C by Martin/Hopkins Calculation

All sensitivity analyses will be conducted on the mITT Population.

Sensitivity Analysis 1

The first sensitivity analysis will impute missing data using a control-based pattern imputation model assuming the data are missing not at random (MNAR). The multiple imputation will be performed such that only observations from the placebo group are used to derive the imputation model for missing LDL-C values. Missing data at Day 28 and 84 will be imputed using multiple imputation methodology in two steps. Initially, 25 data sets will be imputed for non-monotone missing values in the original dataset. In the second step the remaining monotone missing values will be imputed. Upon completion of the trial, if the percentage of cases with incomplete data is larger than initially anticipated then the number of imputations will be increased for the final analysis.

The variables for the imputation model will consist of LDL-C values from baseline and Days 28 and 84. For each imputation dataset, the percent change from baseline to Day 84 will be analyzed using the MMRM model described above for the primary analysis. The results from these 25 analyses will be combined using Rubin's method to construct the treatment estimates using the parameter estimates and associated standard errors. Similarly, the difference of the adjusted treatment means (combination treatment – placebo) will be presented with the associated standard error and 95% confidence interval. Randomly chosen seed numbers will be selected for the analysis and will be retained.

Example SAS code to create a dataset for non-monotone missing values is shown below:

```
*****
```

Note:

non-MONOTONE missing values

TREATMENT = 0 (Placebo), 1 (Obicetrapib monotherapy), 2 (Combination therapy)

LDLC_BASE = LDL_C Baseline value

LDLC_Day28 = LDL_C value at Day 28

LDLC_Day84 = LDL_C value at Day 84

```
*****
```

```
proc mi data=LDLC_Wide seed=18032021 out=LDLC_25MCMC n impute=25;
```

```
  var TREATMENT LDLC_base LDLC_Day28 LDLC_Day84;
```

```
  mcmc impute=monotone chain=multiple;
```

```
run;
```

```
*****
```

In the second step, the remaining monotone missing values will be imputed. Example SAS code to complete this step is shown below:

```
*****
```

Note:

MONOTONE missing values

TREATMENT = 0 (Placebo), 1 (Obicetrapib monotherapy), 2 (Combination therapy)

LDLC_BASE = LDL_C Baseline value

LDLC_Day28 = LDL_C value at Day 28

LDLC_Day84 = LDL_C value at Day 84

```
*****
```

```
proc mi data= LDLC_25MCMC seed=810456 out= LDLC_Mono n impute=1 simple;
```

```
  monotone method=reg;
```

```
  class TREATMENT;
```

```
  var LDLC_base LDLC_Day28 LDLC_Day84;
```

```
  by _Imputation_;
```

```
  mnar model (LDLC_Day28 LDLC_Day84 / modelobs=(TREATMENT=0);
```

```
run;
```

```
*****
```

For each imputation dataset, the percent change from baseline to Day 84 will be analyzed using a similar MMRM approach. Then the parameter estimates will be combined using Rubin's method. Example SAS code to combine the parameter estimates is shown below:

```
*****
```

Note:

MIANALYZE to combine imputations

```
*****
```

```
proc mianalyze parms(classvar=full)=mixLSM;
```

```
  class TREATMENT;
```

```
  modeleffects TREATMENT;
```

```
  ods output parameterestimates=mi_LSM;
```

```
run;
```

```
proc mianalyze parms(classvar=full)=mixDIFF;
```

```
  class TREATMENT;
```

```
  modeleffects TREATMENT;
```

```
  ods output parameterestimates=minus_mi_DIFF;
```

```
run;
```

```
*****
```

Sensitivity Analysis 2

In the second sensitivity analysis, the percent change from Day 1 to Day 84 in LDL-C (as determined by approach 1 above) for the combination treatment group compared to the placebo group will be analyzed using an ANCOVA model with fixed effects of treatment group and the baseline LDL-C value as a continuous covariate. The least squares means, standard errors, and 2-sided 95% confidence intervals for the combination treatment group and for the comparison of the combination treatment group to the placebo group will be provided. The treatment comparison (combination treatment – placebo) will be performed using a 2-sided test at the $\alpha = 0.05$ level of significance. No imputation of missing data will be performed for this sensitivity analysis.

Example SAS code can be found below:

```
*****
Note:
USUBJID = unique subject identifier
TREATMENT = 0 (Placebo), 1 (Obicetrapib monotherapy), 2 (Combination therapy)
BASE = Baseline value
PCHG = Percent change from Baseline
*****
proc glm data=LDL_C;
  class TREATMENT;
  model PCHG = TREATMENT BASE / ss1 ss3;
  means TREATMENT;
  lsmeans TREATMENT / cov stderr pdiff cl;
  estimate "Combination - Placebo"      TREATMENT -1 0 1;
run;
*****
```

Sensitivity Analysis 3

In the third sensitivity analysis, the percent change from Day 1 to Day 84 in LDL-C will be assessed where the LDL-C values will be measured by PUC. The percent change from Day 1 to Day 84 in LDL-C by PUC for the combination treatment group compared to the placebo group will be analyzed using an ANCOVA model similar to the model described in the second sensitivity analysis. No imputation of missing data will be performed for this sensitivity analysis.

Sensitivity Analysis 4

In the fourth sensitivity analysis, the percent change from Day 1 to Day 84 in LDL-C will be assessed where the LDL-C values will be derived using the Martin/Hopkins calculation. A similar MMRM model as described for the primary analysis will be used.

